 - b. First dose of rituximab 375mg/m² administered (premedication with hydrocortisone 100mg IV, diphenhydramine 25-50mg IV or PO, acetaminophen 650mg PO)
 - c. Prednisone 60mg daily continued
 - d. Focused history and physical exam performed by one of the investigators
 - e. BVAS/WG and Vasculitis Damage Index (VDI) assessed by one of the investigators
 - f. Adverse events assessed by one of the investigators
3. Study visit 2 – one week after first study visit
 - a. Second dose of rituximab 375mg/m² administered (premedication with hydrocortisone 100mg IV, diphenhydramine 25-50mg IV or PO, acetaminophen 650mg PO)
 - b. Prednisone 60mg daily continued
4. Study visit 3 – two weeks after first study visit
 - a. Third dose of rituximab 375mg/m² administered (premedication with hydrocortisone 100mg IV, diphenhydramine 25-50mg IV or PO, acetaminophen 650mg PO)
 - b. Prednisone decreased to 40mg daily

- c. Laboratory tests – CBC, CMP, ESR, CRP, urinalysis
5. Study visit 4 – three weeks after first study visit
 - a. Final dose of rituximab 375mg/m² administered (premedication with hydrocortisone 100mg IV, diphenhydramine 25-50mg IV or PO, acetaminophen 650mg PO)
 - b. Prednisone 40mg daily continued
6. Study visit 5 – four weeks after first study visit
 - a. Patient assessed for disease response defined as:
 - i. no new disease manifestations
 - ii. no worsening of existing disease
 - iii. stable or improved BVAS/WG score
 - b. Focused history and physical exam performed by one of the investigators
 - c. Adverse events assessed by one of the investigators
 - d. Prednisone decreased to 30mg daily if disease response is achieved
 - e. Laboratory tests – CBC, CMP, ESR, CRP, ANCA, urinalysis, B-cell flow cytometry
7. Phone call – five weeks after first study visit
 - a. Phone assessment for any new or ongoing symptoms performed by one of the physicians, research nurse or study coordinator
 - b. Prednisone decreased to 20mg if no new symptoms
 - c. Schedule urgent visit if new or worsening symptoms
8. Phone call – six weeks after first study visit
 - a. Phone assessment for any new or ongoing symptoms performed by one of the physicians, research nurse or study coordinator
Prednisone decreased to 10mg if no new symptoms
 - b. Laboratory tests – BMP, ESR, CRP, urinalysis
 - c. Schedule urgent visit if new/worsening symptoms or worsening laboratories
9. Phone call – seven weeks after first study visit

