 - a. Phone assessment for any new or ongoing symptoms performed by one of the physicians, research nurse or study coordinator
Prednisone decreased to 5mg if no new symptoms
 - b. Schedule urgent visit if new or worsening symptoms
10. Study visit 6 – eight weeks after first study visit
 - a. Patient assessed for partial disease remission defined as:
 - i. no new disease manifestations
 - ii. no worsening of existing disease
 - iii. BVAS/WG < 3
 - b. Adverse events assessed by one of the investigators

- c. Prednisone discontinued (or reduced to patient's stable chronic dose of prednisone in order to avoid adrenal insufficiency) if patient meets partial disease remission criteria Omeprazole discontinued
 - d. Laboratory tests – CBC, CMP, ESR, CRP, ANCA, urinalysis, B-cell flow cytometry
11. Phone call – nine weeks after first study visit
- a. Phone assessment for any new or ongoing symptoms performed by one of the physicians, research nurse or study coordinator Laboratory tests – CBC, CMP, ESR, CRP
 - b. Schedule urgent visit if new/worsening symptoms or worsening laboratories
12. Study visit 7– twelve weeks after first study visit
- a. Focused history and physical exam performed by one of the investigators
 - b. BVAS/WG assessed by one of the investigators
 - c. Adverse events assessed by one of the investigators
 - d. Laboratory tests – CBC, CMP, ESR, CRP, ANCA, urinalysis
13. Phone call – sixteen weeks after first study visit
- a. Phone assessment for any new or ongoing symptoms performed by one of the investigators
 - b. Laboratory tests – CBC, CMP, ESR, CRP, ANCA, and urinalysis
 - c. Schedule urgent visit if new/worsening symptoms or worsening laboratories
14. Study visit 8 – twenty weeks after first study visit
- a. Focused history and physical exam performed by one of the investigators
 - b. BVAS/WG assessed by one of the investigators
 - c. Adverse events assessed by one of the investigators
 - d. Laboratory tests – CBC, CMP, ESR, CRP, ANCA, urinalysis
15. Study visit 9 – twenty-four weeks after first study visit
- a. Focused history and physical exam performed by one of the investigators
 - b. BVAS/WG and VDI assessed by one of the investigators
 - c. Primary outcome measured - defined as BVAS/WG = 0 and prednisone dose = 0 (or maintained at patient's stable chronic dose of prednisone in order to avoid adrenal insufficiency) with no preceding flares.
 - d. Adverse events assessed by one of the investigators

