 - e. Laboratory tests – CBC, CMP, ESR, CRP, ANCA, urinalysis, B-cell flow cytometry, immunoglobulin levels (IgG, IgM and IgA).

Following the completion of six months on protocol, subjects will be treated according to the best medical judgment of their treating physician and will continued to be followed for six additional months.

16. Study visit 10 – 9 months after first study visit
 - a. Focused history and physical exam performed by one of the investigators
 - b. BVAS/WG assessed by one of the investigators
 - c. Adverse events assessed by one of the investigators
 - d. Laboratory tests – CBC, CMP, ESR, CRP, ANCA, urinalysis, B-cell flow cytometry
17. Study visit 11 – 12 months after first study visit
 - a. Focused history and physical exam performed by one of the investigators
 - b. BVAS/WG and VDI assessed by one of the investigators
 - c. Adverse events assessed by one of the investigators
 - d. Sustained remission assessed – defined as BVAS/WG = 0, prednisone dose = 0 (or maintained at patient’s stable chronic dose of prednisone in order to avoid adrenal insufficiency) and no disease flares during the study period.
 - e. Laboratory tests – CBC, CMP, ESR, CRP, ANCA, HACA, urinalysis, B-cell flow cytometry, immunoglobulin levels (IgG, IgM and IgA)

Additional visits may be required at the discretion of the investigator.

Missed visits

- If a subject is unable to attend a scheduled visit they may reschedule within 10 days of the time specified by the protocol.
- If a subject cannot attend a scheduled visit within 10 days of the date specified by the protocol a phone call and laboratory testing may be substituted on up to two occasions over the one year study period. The phone call will include a focused history and BVAS/WG scoring.

Mechanistic study

Subjects may be asked to give a blood sample for mechanistic studies, not to exceed 40ccs at the beginning of the study, at the 6 month timepoint, at the completion of the study and during disease flares.

Reimbursement

- Subjects will be given a \$40.00 echeck for each study visit.

Treatment of flares

Limited flares - having a new occurrence or worsening of one or more minor BVAS/WG items with a total BVAS/WG score < 3.

- First limited flare - prednisone increase up to 40 mg/day for one week followed by 4 week taper (30mg, 20mg, 10mg, 5 week per week). Lower starting

prednisone dose and shorter taper can be instituted at the discretion of the investigator.

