- Grade 3 = Severe and undesirable adverse event
- Grade 4 = Life-threatening or disabling adverse event
- Grade 5 = Death

VI. Statistical Analysis

The following variables will be collected during the study:

- Baseline variables
 - o Age
 - o Sex
 - o Disease type (GPA or MPA)
 - o ANCA type
 - o New or relapsing disease
 - o If relapsing disease - treatment prior to flare
 - o BVAS/WG
 - o VDI
- BVAS/WG at visits 1 and 5-11
- VDI at visits 9 and 11
- Laboratory data at baseline and at visits 3, 5, 6, 7, 8, 9, 10 and 11 and after phone calls at 6,9 and 16 weeks of the study
 - o CBC
 - o CMP
 - o ESR
 - o CRP
 - o ANCA
 - o Urinalysis
 - o Flow cytometry for B-cells (measured at visits 1, 5, 9, 10, 11)
 - o HACA (measured at visits 1, 9, 11)
 - o Quantitative immunoglobulins (measured at visits 1, 9 and 11)
 - o Mechanistic studies (optional) (visit 1, 9, 11)
- Prednisone dose at each visit
- Adverse events

Study endpoints

Primary endpoint (assessed at 24 weeks) - Number of patients entering remission defined as BVAS/WG = 0 and prednisone dose = 0 (or maintained at patient's stable chronic dose of prednisone in order to avoid adrenal insufficiency).

Secondary endpoints (assessed at 24 weeks)

- Number of early treatment failures defined as patients who have new or worsening disease manifestations assessed at 4 weeks after study entry
- Number of severe flares defined as flare with BVAS/WG ≥ 3 or experiencing one of the major BVAS/WG items
- Number of limited flares defined as having a new occurrence or worsening of one or more minor BVAS/WG items
- Number of patients having a disease response
- Number of patients entering partial remission
- Number of patients entering sustained remission defined as BVAS/WG = 0, prednisone dose = 0 (or maintained at patient's stable chronic dose of prednisone in order to avoid adrenal insufficiency) and no disease flares during the study period.
- Area under the curve BVAS/WG

- Total GC dose

Statistical Methods

Continuous data will be summarized using descriptive statistics (e.g., mean, standard deviation, median, minimum, and maximum). Categorical data will be assessed using the Chi-square and the Fisher exact tests as appropriate. Descriptive statistics and two-sided 95% confidence intervals will be calculated to assist in the interpretation of efficacy outcomes.

Power Analysis

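### The missed-visit rule lets BVAS/WG be scored by phone at Visit 9, where it decides the primary outcome, and the plan does not say how such a score counts

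*Combined protocol and SAP*

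**What the plan says.** - **Section V.A, Missed visits.** For a patient who cannot attend, "they may reschedule within 10 days of the time specified by the protocol". If that is not possible, "a phone call and laboratory testing may be substituted on up to two occasions over the one year study period". The rule applies to scheduled visits in general and excepts none. On what the substitute covers, it says: "The phone call will include a focused history and BVAS/WG scoring". It mentions no examination, names no scorer and does not list the tests.
- **Section V.A, Study visit 9 (week 24).** An investigator takes a focused history, examines the patient, and scores BVAS/WG and VDI. "Primary outcome measured - defined as BVAS/WG = 0 and prednisone dose = 0", with an allowance for a stable chronic prednisone dose and the condition that no flare came before. The visit's laboratory list includes urinalysis.
- **Section VI.** The variables list plans "BVAS/WG at visits 1 and 5-11" and does not separate examined from phone scores. The primary endpoint is the number in remission at 24 weeks, and the methods are descriptive statistics with two-sided 95% confidence intervals. Nothing is said about a phone-scored Visit 9. The sample is 20 patients, chosen for convenience.
- **Section V.A, after Study visit 11.** "Additional visits may be required at the discretion of the investigator".

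**The concern.** The protocol ties the score to an examination. Entry BVAS/WG is confirmed by history and physical examination, and at Visits 1 and 7 to 11 an investigator's examination is listed with an investigator's score. The substitute call keeps the history, the score and the laboratory tests, but it cannot include the examination.

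This matters most at Visit 9, because the primary outcome requires a score of exactly 0. One active item that only an examination would show is enough to turn a true failure into a counted remission. The opposite error is possible, for example a reported symptom that an examination would have explained otherwise, but a score built on less information is more likely to be too low than too high. The protocol describes no control group in which such an error could cancel.

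**Working it through.** The plan gives no figure to reproduce: there is no power calculation, and no rate of missed visits. The check is a comparison of texts, followed by a scale calculation on stated assumptions.

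**1. Does the rule reach Visit 9?** Yes. Neither the missed-visit rule, the Visit 9 entry nor section VI excludes it.

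**2. How old could the last scheduled examination be?** If only Visit 9 is by phone, it is Visit 8 at week 20, 24 − 20 = 4 weeks earlier. If both permitted substitutions fall on Visits 8 and 9, it is Visit 7 at week 12, 24 − 12 = 12 weeks earlier.

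**3. Which failures could a phone score hide?** Only those that rest on disease activity at week 24 alone. A patient with a known earlier flare, or still on prednisone above the permitted dose, fails the Visit 9 definition whatever the score.

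**4. Average inflation.** All four inputs are assumptions.

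| Input | Low | High |
|---|---|---|
| f: share of Visit 9s by phone | 5% | 20% |
| q: true non-remission | 20% | 40% |
| a: share of q failing only on week-24 activity | 20% | 50% |
| m: share of those missed by phone | 25% | 50% |

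Inflation p = f × q × a × m.

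- Low: 0.05 × 0.20 × 0.20 × 0.25 = 0.0005, or 0.05 points.
- High: 0.20 × 0.40 × 0.50 × 0.50 = 0.02, or 2.0 points.

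The chance that at least one of 20 patients is misclassified is 1 − (1 − p)^20, which is 1.0% (low) and 33.2% (high). The high figure needs all four inputs at their maximum.

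**5. One patient.** 1/20 = 5 points. For illustration, with exact (Clopper-Pearson) 95% intervals:

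- 14/20 = 70% (45.7 to 88.1), width 88.1 − 45.7 = 42.4 points.
- 15/20 = 75% (50.9 to 91.3).

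Section IX stops the study if 60% fail the primary endpoint. If that is applied at the ten-patient review, one false remission turns 6/10 failures into 5/10.

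**6. Sensitivity analysis.** Suppose 14/20 remissions are reported. If one was scored by phone, counting it as not in remission gives 13/20 = 65% (40.8 to 84.6). If two were, 12/20 = 60% (36.1 to 80.9).

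**7. Why this should not be the primary analysis.** Counting every phone-scored patient as a failure also removes true remissions. Against the true rate, the loss is 0.05 × 0.80 = 4.0 points (low) and 0.20 × 0.60 = 12.0 points (high). Against the reported rate in the high case, the result falls from 60 + 2 = 62% to 0.80 × 60 = 48%, or 14 points. Either way this exceeds the error being corrected.

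**The case against.** **The fallback is reasonable for a small pilot.** It applies only after a 10-day window, at most twice per patient, and avoids missing data. Laboratory testing continues, the investigator may call for more visits, and Visit 8 has an examination four weeks earlier. This stands, and it is why the average effect is probably small. It does not settle how a phone-scored Visit 9 counts.

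**A reader might infer that a nurse or coordinator would score by phone,** since some calls are "performed by one of the physicians, research nurse or study coordinator". The documents do not support this. Those are symptom calls with no BVAS/WG, and wherever a BVAS/WG assessor is named it is an investigator. What stands is that the rule names nobody, which one clause would cure.

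**A reader might infer a comparable hazard at Visit 6,** where prednisone stops "if patient meets partial disease remission criteria". That reading is weak. The criterion is BVAS/WG < 3, so prednisone may stop at a score of 1 or 2 even in person. The Visit 6 entry lists no examination, and the cuts to 20, 10 and 5 mg are made by phone by design. Holding 5 mg until a later examination would depart from the 8-week course under test.

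**The score is used at other visits too.** Visits 5, 7, 8 and 11 rely on it for response, flares or sustained remission, and the rule exempts none of them. Visit 9 is singled out because the primary outcome is measured there.

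**A fixed later window, for example to week 28, is also tempting.** But the endpoint is set at 24 weeks, and treatment is at the physician's judgment after six months. New treatment could create or mask a failure, and recording it would not undo that.

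**Conclusion.** The point holds in a limited form. The rule permits an unexamined score to decide the primary outcome, leaves its handling in the analysis unstated, and has a likely error in favour of remission. That no examination takes place is inferred from the format and listed content of the call; the text does not say so outright.

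The size cannot be derived from the documents. On the assumptions above, the average effect is 0.05 to 2.0 points and the chance of any misclassification is 1% to 33%. That is minor beside an interval about 42 points wide, although a single patient moves the result by 5 points. A reader might infer that the primary result is materially biased. The documents do not support that: they give no rate of use, and the range rests wholly on assumed inputs. This is an inexpensive improvement, not a defect that undermines the trial.

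**What to change.** Add to the missed-visit rule and to section VI:

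1. For Visit 9, phone substitution is a last resort. The in-person examination is rescheduled as close to week 24 as possible, and its date and any treatment change after week 24 are recorded. The team should say in advance what still counts as near week 24; the documents give no basis for a particular limit beyond the present 10 days.
2. If no examination can be obtained near week 24, the primary analysis uses a phone score made by an investigator, flagged as such.
3. The report gives the number of phone-scored Visit 9s, with a sensitivity analysis counting those patients as not in remission.

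The cost is a few sentences, a few slightly late primary assessments and one extra analysis. Phone follow-up at other visits stays as it is. A late examination may follow a treatment change; recording this makes it visible but does not remove it, which is why the examination should stay close to week 24.

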The primary aim of this pilot study is to examine whether an 8 week course of GCs in combination with rituximab is effective at inducing and maintaining disease remission through the 6-month timepoint in patients a subset of patients with AAV who have a more favorable prognosis.

III. Subject Selection

A. Inclusion and exclusion criteria

Inclusion criteria:

- Patients ages 18-85 years old
- Diagnosis of GPA or MPA according to the definitions of the Chapel Hill Consensus Conference
- New diagnosis or disease flare with a Birmingham Vasculitis Activity Score/Wegener's granulomatosis (BVAS/WG) of ≥ 3 .

Exclusion criteria:

- Renal disease in patients with PR3-ANCA as defined by any of the following:
 - Urinary red blood cell casts
 - Biopsy-proven glomerulonephritis
 - Increase in serum creatinine of $>30\%$ over baseline
- Severe renal disease in patients with MPO-ANCA as defined by both of the following:
 - Urinary red blood cell casts or biopsy-proven glomerulonephritis
 - Estimated glomerular filtration rate < 30 ml/min/1.73m²
- Diffuse alveolar hemorrhage requiring ventilatory support
- GC treatment for longer than 14 days prior to enrollment unless patient has been on a stable maintenance dose of prednisone at the time of the flare

- Daily oral cyclophosphamide within 1 month prior to enrollment
- Completed a remission induction course of cyclophosphamide or rituximab within 4 months of enrollment
- Current or past HBV infection (e.g., HBsAg positive, regardless of antibody status, HBsAg negative but anti-HBcAb positive).
- HIV infection
- History of anti-GBM disease
- Other uncontrolled disease, including drug and alcohol abuse, that may interfere with the study
- Pregnancy or breastfeeding
- History of severe allergic reactions to human or chimeric monoclonal antibodies

B. Source of subjects and recruitment methods

Subjects will be recruited via one of the following:

- New diagnosis or flare of previously diagnosed disease in patients followed in the Massachusetts General Hospital (MGH) Rheumatology or Nephrology Units.
- New diagnosis or flare of previously diagnosed disease in patients hospitalized at MGH.
- Referrals from subspecialty colleagues who are aware of our interest in AAV.

IV. Subject Enrollment

A. Methods of enrollment and procedures for obtaining informed consent.

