- Drs. [name], [name], [name] or [name] will discuss various treatment modalities with patients meeting the inclusion criteria. In addition to the study treatment protocol, the following treatment options will be discussed: Rituximab and conventional duration of GC therapy (6-12 months); cyclophosphamide and conventional duration of GCs, followed by azathioprine or methotrexate. Patients will be given adequate time to ask questions related to various treatment options and to discuss the study procedures in detail.
- Informed consent will be discussed with all potential study subjects by Drs. [name], [name], [name] or [name]. In addition to the physicians, a nurse or coordinator will be available to answer patient's questions.
- Patients will be given up to seven days to consider treatment options.

V. Study Procedures

A. Study visits and data collection

1. Screening visit
 - a. Diagnosis of new onset AAV or flare with BVAS/WG ≥ 3 will be confirmed by a complete history and physical examination performed by one of the investigators.
 - b. Treatment options will be discussed with the patient and informed consent for study participants will be obtained by one of the investigators.
 - c. The following laboratory values will be obtained – complete blood count (CBC), complete metabolic panel (CMP), erythrocyte sedimentation rate (ESR), C-reactive protein (CRP), ANCA, chronic hepatitis B infection panel, HIV antibody, B-cell flow cytometry, immunoglobulin levels (IgG, IgM and IgA), urinalysis and urine pregnancy test if applicable.
 - d. Imaging as deemed necessary by the investigator
 - e. Patients will begin GC therapy at a dose selected by the investigator or the treating physician with oral prednisone 60mg or 1mg/kg (if weight less than 60kg) or intravenous methylprednisolone, up to 1g/day for three days.
 - f. Patients will be started on omeprazole 20mg daily, trimethoprim-sulfamethoxazole one single strength tablet daily, calcium citrate 500mg twice daily and vitamin D 400 units twice daily.
 - g. Prior clinical assessment (labs) within one year can be used to determine screen eligibility.
2. Study visit 1 (no later than 14 days after the screening visit)
 - a. Treatment options will be discussed with the patient and informed consent for study participants will be obtained by one of the investigators.
 - i. All screening laboratory values must be completed

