- Second limited flare - treatment according to best medical judgment of the investigator.

Severe flares – BVAS/WG ≥ 3 or experiencing one of the major BVAS/WG items.

- Patients with severe flares will be treated according to best medical judgment of the investigator.

Termination of protocol

The following pre-defined events will lead to subject's treatment according to best medical judgment:

- Two limited flares - defined as having a new occurrence or worsening of one or more minor BVAS/WG items.
- One severe flare - defined as BVAS/WG ≥ 3 or experiencing one of the major BVAS/WG items)
- Failing to achieve disease response at 4 weeks following the first rituximab infusion - defined as no new disease manifestations, no worsening of existing disease and stable or improved BVAS/WG score
- Failing to achieve partial remission at 8 weeks following the first rituximab infusion - defined as no new disease manifestations, no worsening of existing disease and BVAS/WG < 3 .

Subjects treated according to best medical judgment will continue to be followed according to a modified visit schedule of no less than once every three months for 12 months from study entry.

Data Collection

Data, including BVAS/WG scores, blood and urine test results, relevant radiology and pathology findings will be kept on data collection sheets and on Partners workstations or encrypted mobile devices using unique patient identifiers. Drs. [name], [name], [name], [name] as well as [name], [name], [name] and study staff will have access to coding sheets linking patient names and their unique identifiers. The data collection sheets will be kept in a locked file cabinet in the Rheumatology Unit.

Drs. [name] and [name] will review data on the number of subjects having limited or severe flares, achieving disease response, achieving partial remission and achieving remission after the first ten patients have been followed for six months. [name] will be responsible for determining whether the research should be altered or stopped.

PI's intention is to maintain the subject files electronically through utilizing a Redcap database as well as accessing additional information from LMR. The current Redcap

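### The limited-flare definition loses its ceiling of 3 in the Termination list and Section VI, so a minor-item flare totalling 3 or more counts as both limited and severe

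*Combined protocol and SAP*

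**What the plan says.** Each flare type is defined in three places of the combined protocol and SAP.

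**Limited flare.** Section V, Treatment of flares, asks for two things: a new or worse minor BVAS/WG item, and a total score below 3. Section V, Termination of protocol, has "Two limited flares - defined as having a new occurrence or worsening of one or more minor BVAS/WG items", with no limit on the total. The secondary endpoint in Section VI repeats the Termination wording, also without the limit.

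**Severe flare.** Treatment of flares has "Severe flares – BVAS/WG ≥ 3 or experiencing one of the major BVAS/WG items". The Termination list has "One severe flare - defined as BVAS/WG ≥ 3 or experiencing one of the major BVAS/WG items". Neither asks for anything new or worse. Section VI uses the same two limbs but puts the word flare in front of the score.

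**Where the labels are used.** One severe or two limited flares end protocol treatment (Termination) and count as failure in the study stopping rule (Section IX). Section VI lists the number of severe flares and the number of limited flares as secondary endpoints. Under Data Collection in Section V, limited and severe flares are tallied again once ten patients have six months of follow-up.

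**The concern.** A patient with one new minor item and a total of 3 or 4 has a severe flare, and only that, under Treatment of flares. Under Section VI the same event meets both definitions. An analyst who programs Section VI as written will enter it in both counts. The limited-flare count is then too high, the two counts add up to more than the flares that happened, and a reader of the report cannot separate them again. The ten-patient tally is exposed in the same way if it uses the wording without the ceiling.

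The second, smaller issue is the severe definition in Section V. Taken word for word it describes a state, not a change. A patient at week 4 with residual baseline activity and nothing new could be labelled a severe flare and taken off protocol treatment.

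**Working it through.** The documents state no figure on this point that could be reproduced, so the check applies each definition, as written, to every kind of flare.

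**Step 1: the dropped ceiling.** Classify a flare by which items are new or worse (minor only, major only, both) and by the total (below 3, or 3 and above). That gives 3 × 2 = 6 types.

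| New or worse items | Total | Limited: Treatment of flares | Limited: Termination, Section VI | Severe: all three places |
|---|---|---|---|---|
| Minor only | < 3 | yes | yes | no |
| Minor only | ≥ 3 | no | yes | yes |
| Major only | < 3 | no | no | yes |
| Major only | ≥ 3 | no | no | yes |
| Both | < 3 | yes | yes | yes |
| Both | ≥ 3 | no | yes | yes |
| Types covered | | 2 | 4 | 5 |

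- With the ceiling: 2 + 5 = 7 labels for 6 types, so one type is double-labelled (both, total < 3). The documents give no item weights, so this type may not be possible.
- Without it: 4 + 5 = 9 labels for 6 types, so three are double-labelled. Dropping the ceiling adds two: minor only with total ≥ 3, and both with total ≥ 3.
- Severe covers the same 5 types either way.

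**Step 2: effect on the counts.** Let L be the number of limited flares under the ceiling, S the number of severe flares, and k the number of flares of the two added types. Section VI then gives limited = L + k and severe = S, with the k flares already inside S. Leaving aside the type that may not exist, the number of flares is L + S, and the two counts sum to L + S + k. The excess is k.

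Illustration with assumed counts: L = 3, k = 0, 1 or 2, and no other flares, so S = k.

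- Flares that occurred: 3 + k = 3, 4, 5
- Limited count under Section VI: 3 + k = 3, 4, 5, against 3 with the ceiling
- Limited plus severe: (3 + k) + k = 3, 5, 7

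**Step 3: what does not move.** Any flare totalling 3 or more is severe in every version, and one severe flare already ends protocol treatment and already counts as failure in Section IX. Labelling it limited as well changes neither. The visit 9 outcome and sustained remission exclude any flare, so the label is irrelevant there. The primary endpoint in Section VI has no flare clause.

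**Step 4: the severe definition set beside the rest of the plan.**

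- Entry requires a score of at least 3: "New diagnosis or disease flare with a Birmingham Vasculitis Activity Score" in Section III.A, and at screening "Diagnosis of new onset AAV or flare with BVAS/WG ≥ 3 will be confirmed". Read literally, every patient would be in severe flare on the first day.
- At study visit 5 (week 4), response needs nothing new, nothing worse, and a "stable or improved BVAS/WG score". A score still at 3 or more can qualify, and so can a persisting major item. The instruction is then "Prednisone decreased to 30mg daily if disease response is achieved", which continues the protocol taper.
- A score below 3 is first required at week 8, and the Termination list carries that as a separate event: "Failing to achieve partial remission at 8 weeks following the first rituximab infusion". If a persisting score of 3 or more were already a severe flare, the score part of that event would be redundant.
- In Section VI, early treatment failure at week 4 also depends on new or worsening manifestations, and the severe endpoint is worded as a flare with a given score.

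All four point to a change from the patient's earlier state as the intended condition, for the score and for the major item alike.

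**The case against.** The strongest reply on the main point is that the full definition stands directly before the Termination list, so the later wording is shorthand. That is plausible for Termination, where the ceiling makes no difference. It is weak for Section VI, which gives its own complete definition with no reference back and is the text from which the counts will be produced.

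It can also be said that little follows: a descriptive secondary count in a convenience sample of 20. That stands, and it is why the point is minor.

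Three stronger readings are tempting, and the documents do not support them.

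- A reader might infer that the plan really leaves open whether a baseline major item persisting at week 4 is a severe flare, because experiencing an item can include still having it. The evidence in step 4 that makes the score limb a drafting slip applies equally to the major-item limb: the taper of a stable responder makes no exception for a major item, and the word flare in Section VI can govern both limbs. This is a wording defect in Section V, not a second competing rule.
- A reader might express the inflation as a percentage of 20 patients with an exact binomial interval. Section VI counts limited and severe flares, not patients who had them, so neither applies.
- A reader might conclude that no flare wording can touch the Section VI primary endpoint. That is right for the dropped ceiling. It is not strictly right for the literal severe definition: if someone acted on it, treatment would pass to the investigator's judgment, and prednisone could be above 0 at week 24.

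**Conclusion.** The definitions conflict, and the Section VI wording is wrong as it stands. Each flare with a new or worse minor item and a total of 3 or more adds one to the limited-flare count while also being counted as severe. At the ten-patient review, which counts subjects, a patient whose only flare is of this kind would enter the limited tally as well. The size is a number of events, k in the working, and cannot be estimated because the documents contain no flare rates or score distributions; the values shown are assumed. Severe counts, termination and the Section IX failure count are unaffected.

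The missing new-or-worse condition in the Section V severe definition is secondary. Its literal reading would end protocol treatment for week-4 responders with residual activity, which the rest of the plan shows is not intended. It needs correcting so that nobody acts on it.

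Overall this is a minor point. The text conflict is certain; its numerical effect is unknown and confined to descriptive counts.

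**What to change.** Put one definition in Section V and refer to it from Termination, Section VI and Section IX:

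- A flare requires at least one new or worse BVAS/WG item.
- It is severe if a new or worse item is major, or if the total is 3 or more.
- It is limited if only minor items are new or worse and the total is below 3.
- Activity that persists from baseline is judged by the week-4 and week-8 criteria and is not a flare.

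Applied to the six types, this gives limited 1, severe 5, none double-labelled and none unclassified. Treatment after each type of flare stays as written.

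Two downsides should be stated. Residual baseline points can lift a minor flare to severe through the total alone, so flares that are severe only by total should be listed. The week-8 criterion has no major-item clause, so a major item that persists with a total below 3, if the item weights allow it, should be flagged before prednisone is stopped.

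The cost is wording in three sections. The limited-flare definition and the week-4 criteria already require investigators to judge what is new or worse, and the flare definitions already separate minor from major items. No further assessment is needed; the flare record only has to show which items were new or worse.
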